## 9.5 Statistical Analysis Plan

Data analyses will primarily be descriptive. The purpose of this study is to identify a ganaxolone dose and exposure level that is safe and well tolerated. Efficacy data will be collected but will be considered hypothesis-generating i.e., there are no *a priori* hypotheses on which the study was powered. Results from exploratory statistical analyses may be presented but only to aid in interpretation.

The SAP will provide the statistical methods and definitions for the analysis of the safety and efficacy data, and it will describe the approaches to be taken for summarizing other study information such as subject disposition, demographics and baseline characteristics, investigational product exposure, and prior and concomitant medications. The SAP will also include a description of how missing, or unused data will be addressed.

The SAP will be finalized prior to completion of the first cohort to preserve the integrity of the statistical analysis and study conclusions. This will not preclude amendments to the SAP before database lock.

## 9.5.1 **Planned Interim Analysis**

Safety and efficacy data from each cohort will be unblinded, and analyses will be conducted for the purpose of dose selection for the next cohort. The dose for the next cohort will be decided based on these interim data analyses. The decision how to adjust the dose and/or the duration of the infusion will be made based on recommendations by a Data Review Committee (DRC) composed of the sponsor's Chief Medical Officer, and at least 2 other external physicians. At least one of the members will have special expertise in the clinical care of women with depression or postpartum depression. One of the members will have expertise in the conduct of clinical trials or analysis of clinical trial data. The study team and all parties other than the DRC will remain blinded.

The dose for the subsequent cohorts will be selected with the goal of gaining additional information on ganaxolone's tolerability and dose-response profile.

A separate DRC guidance document outlines the principles for dose selection. Marinus may decide to stop the study, or make the data public, after completion of any cohort.

# 9.5.2 Justification for Sample Size

No formal hypothesis testing will be performed and the sample size is not based on statistical power considerations. The sample size was chosen based on experience with other studies conducted with compounds in early clinical development. A population of about 6 to 10 subjects per dose is commonly tested in studies which aim to establish a tolerability range for a new compound or a new formulation, and is used as a guide for a minimum cohort size for this study.

Similar study design was recently used to assess safety and identify an efficacy signal in major depressive disorder for NSI-189.

## 9.5.3 **Study Population**

The Screened Set will consist of all subjects who have signed an informed consent.

The Randomized Set will consist of all subjects randomized.

The Safety Set will consist of all subjects who received IP.

The **modified Intent to Treat Set** (mITT) will consist of all subjects in the Safety Set who have at least 1 post-randomization efficacy assessment.

The **Per-Protocol Set** will consist of all subjects in the mITT set who do not have major protocol deviations that may affect key efficacy endpoints.

The **Infusion Completer Set** will consist of all subjects in the Safety Set who completed the 60-hour infusion in Cohort 1-5, and who completed the initial infusion in Cohort 6.

The **Completer Set** will consist of all subjects in the Safety Set who completed the 60-hour infusion and attended the final safety follow-up visit in Cohorts 1-5. In Cohort 6 the completer set will consist of subjects who completed the initial infusion and oral IP dosing period with at least 80% oral dosing compliance and attended all outpatient visits including the safety follow-up visits.

# 9.5.4 **Demographic and Baseline Characteristics**

Descriptive summaries of demographic and baseline characteristics as well as subject disposition will be presented by treatment group.

Baseline characteristics will include a summary of the following:

- Subject demographics
- Pre-existing medical conditions
- Prior therapies.

Continuous variables such as age, weight, and height will be summarized using number of observations, mean, standard deviation, median, minimum, and maximum values. Categorical variables, like sex and race, will be summarized using number of observations and percentages.

Medical history will be summarized by treatment group using the number of observations and percentages of subjects reporting each category.

# 9.5.5 **Investigational Medicinal Product**

Summary statistics for the duration of exposure to investigational medicinal product will be presented by treatment group.

### CONFIDENTIAL

## 9.5.6 **Concomitant Medication**

Concomitant medications will be listed and summarized by preferred drug name and treatment group.

### 9.5.7 Safety Analyses

Reported AE terms will be coded using the Medical Dictionary for Regulatory Activities (MedDRA). The incidence of Treatment Emergent AEs (TEAEs), defined as any AE that started or worsened after first administration of IP, will be summarized by treatment group, system organ class preferred terms, severity and relatedness for each cohort. SAEs and AEs leading to discontinuation of the study drug will be listed separately for each cohort.

The absolute values and change from baseline in laboratory tests, vital signs, SSS, ECGs and CSSRS will be summarized by treatment group for each cohort.

Potentially clinically important findings will be included in AE summaries and listings.

Results of the physical examination (baseline and discharge) will be listed.

### 9.5.8 Efficacy Analyses

### 9.5.8.1 Primary Endpoint

The primary efficacy endpoint will be HAMD17 total score change from baseline to 60 hours post-infusion (on Day 3) for Cohorts 1-3 and to Day 29 for Cohort 6. The primary analysis in each cohort will be done using the mITT set. Although the trial is not powered for inferential analysis and there is no consideration for control of type 1 error across multiple cohorts, a clinically meaningful numeric difference in means of 3-4 points between ganaxalone and placebo treatment groups would be considered an indication of efficacy and will be the most influential outcome in the overall assessment of the efficacy of ganaxalone in treating PPD.

### 9.5.8.2 Secondary Endpoints

The trial will also evaluate the following secondary endpoints at each post-baseline data collection time point to provide additional evidence of the efficacy of ganaxalone in treating PPD:

- Change from baseline in HAMD17 total score other than at 60 hours post-infusion (on Day 3) for Cohorts 1-3 and to Day 29 for Cohort 6
- HAMD17 response defined as at least a 50% reduction from baseline in total score
- HAMD17 remission defined as total score <= 7
- Change from baseline in EPDS total score
- Change from baseline in STAI6
- CGI-I

## 9.5.8.3 Exploratory Endpoints

# 9.5.8.4 Statistical Methods

Observed values and changes from baseline for HAMD17, EPDS, and STAI6 total scores, subscales, and individual items will be summarized by visit. The categorical outcomes of HAMD17 response, HAMD17 remission, and CGI-I will be summarized by visit.

The preferred approach for exploratory analysis of continuous efficacy variables will be mixed model repeated measures (MMRM) but other approaches such as t-tests, analysis of covariance, or non-parametric methods may be used if necessary or more practical. Similarly, the preferred approach for analysis of categorical efficacy variables will be repeated measures (e.g., generalized estimating equations) but other approaches such as chi square or Fisher's exact tests may be used.

### 9.5.9 Other Analyses

No other analyses are planned in this study.

# 9.5.10 Pharmacokinetic Analyses

The following pharmacokinetics parameters will be estimated for each subject receiving ganaxolone, if sufficient data are available: Maximal plasma concentration ( $C_{max}$ ), concentration at steady-state ( $C_{ss}$ , determined by the mean concentrations once steady-state is achieved by visual inspection), AUC0-24 (calculated as  $C_{ss}$  multiplied by 24 hours). PK samples will be collected from subjects participating in Cohort 6 after the IV infusion, before and during the oral dosing portion of the study.

CONFIDENTIAL

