- 11. Subject has untreated or uncontrolled hypothyroidism
- 12. Known or suspected intolerance or hypersensitivity to the investigational product(s) or allopregnanolone, or any of the stated ingredients
- 13. Use of another investigational product within 60 days prior to the first dose of investigational product
- 14. Has alanine transferase (ALT) or aspartate transferase (AST) greater than 2.5 times upper limit of normal or total bilirubin greater than 1.5 times upper limit of normal (unless elevation is due to Gilbert's syndrome)
- 15. Screening QTcF > 470 msec
- 16. Unwillingness to withhold grapefruit, Seville oranges, star fruit, or citrus derived products from diet between screening and discharge from the study unit
- 17. Receiving concomitant treatment with strong CYP3A4 inducers or strong CYP3A4 inhibitors
- 18. Body mass index (BMI)  $\ge 40$
- 19. Subject is pregnant
- 20. Subject is using prohibited medications as specified in Section 5.3.2

Maximum duration of subject involvement in the study: Approximately 12 weeks

**Safety:** Adverse events, vital signs, Columbia Suicide Severity Rating Scale (CSSRS), electrocardiogram (ECG), Stanford Sleepiness Scale (SSS), and physical examination.

**Efficacy:** Hamilton Depression Rating Scale (HAMD17), Edinburgh Postnatal Depression Scale (EPDS), Spielberger State-Trait Anxiety Inventory six item version (STAI6) and Clinical Global Impression-Improvement (CGI-I) scale.

**Pharmacokinetics:** Six samples will be collected for pharmacokinetic analysis in Cohorts 1-5 and 12 samples in Cohort 6. Maximal plasma concentration ( $C_{max}$ ), concentration at steady-state ( $C_{ss}$ , determined by the mean concentrations once steady-state is achieved by visual inspection), AUC0-24 (calculated as  $C_{ss}$  multiplied by 24 hours) will be estimated. Seven samples will be collected during the inpatient phase of Cohort 6 (including 6 samples on Day 1) followed by collection of 5 samples during the outpatient phase during the study visits for a total of 12 samples in Cohort 6.

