#### 3.4 Dose Selection

#### 3.4.1 **Cohort 1**

For Cohort 1, the targeted ganaxolone plasma concentration at steady state ( $C_{ss}$ ) will be 52 ng/ml, which is estimated to be achieved with a ganaxolone infusion rate of 4 mg/hr (16 ml/h of ganaxolone 0.25 mg/ml solution). Steady state is expected to be achieved within 24 hours.

For Cohort 1, the infusion rate is lowered to 2 mg/h after + 48 hours of infusion and stopped at + 60 hours. This is done to minimize any risks for withdrawal or rebound of anxiety and depression symptoms.

The target ganaxolone exposure level of approximately 52 ng/ml for Cohort 1 was chosen to achieve a level similar to that of allopregnanolone at the end of pregnancy. Allopregnanolone levels increase gradually throughout pregnancy reaching a peak mean concentration at the end of pregnancy of about 15 to 60 ng/ml. The levels then drop precipitously after the delivery. We hypothesize that substitution of the low allopregnanolone levels with ganaxolone would alleviate or reverse the symptoms of PPD.

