#### 3.4.5 **Cohort 6**

For Cohort 6, the goal of initiation of treatment with IV infusion followed by oral capsules is to maximize the speed of onset of antidepressant activity while providing the convenience of oral dosing for the remainder of the treatment period. Under this IV-oral dosing schedule there may not be a need for a prolonged inpatient observation.

This initial infusion is targeted to provide a fast onset of antidepressant activity by delivery of rapid plasma exposures to ganaxolone. At dinner time of Day 1 the subjects will take their first oral dose of ganaxolone 900 mg or matching placebo (4 capsules). This dose is expected to provide mean  $C_{max}$  plasma concentrations of approximately 250-300 ng/mL and mean steady-state levels between 90 and 150 ng/mL, which may be mildly sedating. In previous studies ganaxolone has been given up to a daily dose of 2000 mg, and at single doses of 1000 mg. Based on the previous experience this dose is expected to be safe.

At subsequent nights (Days 2-28), the target dose is ganaxolone 900 mg or matching placebo (4 capsules) at dinner time followed by a 3-day taper (3, 2, and 1 capsule/s per day, respectively). However, based on the assessment of the investigator the dose may be maintained at 675 mg or 450 mg (or matching placebo) in case of adverse events, such as grogginess in the morning. In the case of 3 capsules per day on day 28 the taper will consist of 2, 2, and 1 capsule/s on days 29, 30, and 31, respectively. In the case of 2 capsules per day on day 28 the taper will consist of 1 capsule on days 29, 30, and 31. If the subject cannot tolerate 450 mg (or matching placebo) per dose the investigator will contact the Medical Monitor to discuss dosing options.

Subjects will be provided with a diary to capture the details of dose administration and associated food intake throughout the treatment period. Subjects will document the number of capsules taken and whether a fatty meal/snack (e.g., fatty yogurt, nuts, avocado) was consumed  $\pm 15$  minutes of taking the capsules.

The mechanism by which ganaxolone is postulated to be efficacious under this dosing regimen is restructuring of sleep architecture. Preclinical studies have shown that allopregnanolone has the capacity to modulate sleep, and disturbed sleep architecture is one of the hallmarks of depression.

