# 7.0 STUDY PROCEDURES

This is a Phase 2A, double-blind, placebo-controlled, multiple-dose escalation study consisting of up to 6 cohorts. In Cohorts 1-5 the IV formulation of ganaxolone will be used while in Cohort 6 both IV and oral formulations will be used. Approximately 200 women with PPD 18 to 45 years of age will be screened to randomize approximately 100 subjects across the up to 6 cohorts. Approximately 10-30 subjects will be randomized into each cohort. Randomized subjects will receive ganaxolone or placebo in a 1:1 ratio. In Cohorts 1-5 the treatment is administered intravenously (with or without an initial bolus) over 60 hours. In Cohort 6 the treatment is initiated with a 6-hour intravenous (IV) infusion followed by oral ganaxolone or matching placebo. Additional subjects may be included into these cohorts or additional cohorts may be added, but will not exceed 100 randomized subjects for the study.

The screening period for each cohort will be up to 2 weeks. Following the screening period, there will be a 4-day inpatient treatment phase at a hospital or clinical pharmacology unit for Cohorts 1-5 during which a 60-hour infusion of ganaxolone or placebo will be administered (with or without bolus dosing). The subjects will be discharged from the unit on the morning of Day 4. There will be 2 safety follow-up visits after inpatient discharge on post-treatment Weeks 1 and 4.

[figure not shown]
In Cohort 6, following the screening period, there will be a 1-day inpatient treatment phase at a hospital or clinical pharmacology unit during which a 6-hour infusion of ganaxolone or matching placebo will be administered initially from 9 am to 3 pm ( $\pm$ 1 hour) before oral dosing is started at 7 pm ( $\pm$ 1 hour). The subjects will be admitted on Day 0 and discharged from the unit in the morning of Day 2. The first dose of oral ganaxolone (4 capsules; 900 mg) or matching placebo will be administered at dinner time (around 7 pm) of Day 1, 4 hours after the end of infusion on Day 1. Oral dosing is continued as outpatient on Days 2-28. The dosing regimen during the outpatient phase of Cohort 6 is 900 mg or placebo (4 capsules) at dinner time daily. A 3-day taper will follow at days 29, 30, and 31, as described in Section 3.4.6. There will be 3 safety follow-up visits after the last dose on post-treatment Weeks 1,4, and 6.

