Start 3-day taper		i la contra c										64	x			.

a Infusion starts at 9 am and ends 6 hours later at 3 pm and is administered at a constant rate of 40 mL/hr.

b Twelve pharmacokinetic samples are collected in Cohort 6:

On Day 1 subjects will have 6 PK samplings: at 1 hour after the end of the 6-hour infusion (i.e., at 4 pm), at 7 pm (just prior to the oral dosing), and at 1, 2, 3, and 4 hours post oral dosing (at 8, 9, 10, and 11 pm) as well at 8 am the following morning (on Day 2) prior to discharge.

A pharmacokinetic sample is also collected on Days 8, 15, 22, 29, and 36 during the study visit.

c All HAMD17 ratings, except the one done at screening, will be conducted by CTNI raters.

 $^{d}$ Q15min health checks are done from the time of start of the infusion to the time of discharge. Pulse oximetry (pO2) must be monitored from the start of the infusion throughout the inpatient period, including during the night when the subject is sleeping. The subject should be awakened if pulse oximetry falls < 91%.

e On Day +1 all efficacy assessments should be conducted first before lab draws, if possible.

f All Day +2 assessments, including PK and neurosteroid levels, are to be done before the subject is discharged from the unit.

The following priority order will be in effect when more than 1 assessment is required at a particular time point: 1) HAMD17 2) CGI-I/CGI-S 3) EPDS 4) STAI6 5) SSS 6) CSSRS 7) vital signs 8) ECG 9) safety labs and neurosteroid level 10) PK sample 11) neurosteroid level 12) urinalysis drug screen and pregnancy test 13) physical examination

All outpatient visits have  $a \pm 3$ -day visit window, except Visits 3 and 5 which have just  $a \pm 1$ -day visit window and Visits 4 and 6 which have  $a \pm 2$ -day visit window.

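### One rule, AUC0-24 = Css × 24, is written for every cohort, but in Cohort 6 (once-daily oral dosing, single visit samples at unstated times) the mean of those samples does not estimate the 24-hour average.

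*Protocol*

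**What the plan says.** Protocol 9.5.10 states that the PK "parameters will be estimated for each subject receiving ganaxolone, if sufficient data are available". It lists Cmax, then Css, "determined by the mean concentrations once steady-state is achieved by visual inspection", then AUC0-24 calculated as Css "multiplied by 24 hours". The Pharmacokinetics paragraph of the synopsis repeats the rule directly after naming Cohort 6: "Six samples will be collected for pharmacokinetic analysis in Cohorts 1-5 and 12 samples in Cohort 6". Neither place makes an exception for Cohort 6, and SAP 4.1 (Changes from Protocol) lists none. SAP 4.0 and 5.0 place PK analysis outside the SAP.

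The two kinds of cohort differ in dosing and sampling:

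- **Cohorts 1-5** receive a constant-rate infusion for 48 hours, then half the rate to 60 hours. Inpatient PK samples are at +12, +24, +48 and +72 h. For Cohort 1, Protocol 3.4.1 says: "Steady state is expected to be achieved within 24 hours".
- **Cohort 6** receives a 6-hour infusion and then capsules. Protocol 7.0 says: "The dosing regimen during the outpatient phase of Cohort 6 is 900 mg or placebo (4 capsules) at dinner time daily", with dinner time at about 7 pm. Day 1-2 samples are at 4 pm, 7 pm, 8-11 pm and 8 am. Beyond that, Table 2 footnote b says: "A pharmacokinetic sample is also collected on Days 8, 15, 22, 29, and 36 during the study visit". No clock time or time since dose is given for these draws.

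Protocol 3.4.5 expects a mean Cmax for the 900 mg oral dose of "approximately 250-300 ng/mL and mean steady-state levels between 90 and 150 ng/mL".

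**The concern.** Css × 24 equals a 24-hour AUC only when Css is the time-average concentration over those 24 hours. During a constant infusion at plateau the curve is flat, so any plateau sample serves. After a once-daily oral dose the concentration rises and falls within each interval, and the protocol's own expected figures put the peak well above the steady-state level. One draw per visit records one point on that curve. Averaging four such points, all probably from the same part of the day, averages that part of the curve and not the whole interval.

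Plasma exposure is a stated objective (Protocol 2.2.3), and the study results are to be used to select a dose and regimen for further development (Protocol 2.1). An oral AUC0-24 produced by this rule would carry a standard label but would depend on when the subject came to clinic.

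**Working it through.** **Cohorts 1-5.** Taking the Cohort 1 target of 52 ng/mL from Protocol 3.4.1, Css × 24 = 52 × 24 = 1248 ng·h/mL. This is coherent as a 24-hour AUC at steady state.

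**Cohort 6: which samples could enter Css.** The first oral dose is at 7 pm on Day 1, 4 hours after a 120 mg infusion (20 mg/h × 6 h), so the Day 1-2 samples are not at oral steady state. The last taper dose is on Day 31, so Day 36 is 5 days after dosing ends. That leaves one sample on each of Days 8, 15, 22 and 29.

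**Inputs from the documents.** Dosing interval 24 h; dose at about 7 pm; Cmax 250-300 and steady-state level 90-150 ng/mL. The peak-to-level ratio therefore runs from 250/150 = 1.67 to 300/90 = 3.33.

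**Assumptions, not in the documents.** One compartment with first-order absorption; ka 0.3-2.0 per hour; 90-150 read as the 24-hour average and 250-300 as the steady-state peak; visit draws 14-20 h after the dose (9 am to 3 pm).

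**Formulas.** With k the elimination rate and the bioavailable dose over volume set to 1:

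- C(t) = ka/(ka − k) × [e^(−kt)/(1 − e^(−24k)) − e^(−ka·t)/(1 − e^(−24ka))]
- Cavg = 1/(24k), and true AUC0-24 = 24 × Cavg
- Rule ÷ truth = 24 × C(t)/AUC0-24 = C(t)/Cavg

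For each ka, k is solved so that Cmax/Cavg equals the chosen ratio.

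**One case in full.** Take ka = 1.0 and Cmax/Cavg = 250/120 = 2.08. This solves to k = 0.1015 per hour (half-life 6.8 h). Cavg = 1/(24 × 0.1015) = 0.410. C(14) = 0.294, so the ratio is 0.294/0.410 = 0.72. C(20) = 0.160, so the ratio is 0.160/0.410 = 0.39.

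**Range over ka 0.3-2.0:**

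| Cmax/Cavg | C/Cavg at 14 h | C/Cavg at 20 h |
|---|---|---|
| 1.67 | 0.85-0.90 | 0.48-0.60 |
| 2.08 | 0.70-0.74 | 0.27-0.44 |
| 2.50 | 0.52-0.62 | 0.14-0.31 |
| 3.33 | 0.26-0.41 | 0.045-0.15 |

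Overall this is about 0.05 to 0.90. In every case the curve has fallen below its average by 12.9 h after the dose, that is, by about 8 am.

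**Other readings change the answer:**

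- *90-150 ng/mL read as a trough.* With a linear rise to Cmax at 2-3 h and log-linear decline to 24 h, a 14 h sample gives 0.88-0.97 of the average and a 24 h sample 0.51-0.76.
- *Half-life 24-48 h.* Samples at 13-22 h give about 0.76-1.04.
- *Early post-dose samples included.* Suppose the draws at 1-4 h and 13 h are averaged with four visit draws at 16 h, all at steady-state height for illustration (ka 0.5-1.0, half-life 4-24 h). The mean is then 1.02-1.38 of the average, an overstatement.

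**The case against.** The strongest defence has four parts.

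- **The formula itself is not at fault.** A true average steady-state concentration times 24 is the 24-hour AUC for any once-daily regimen, oral included. This is correct. The fault lies in how Css is defined and sampled: a plain mean of samples chosen by eye is not a time-average when there are four isolated draws per subject.
- **The sufficiency condition could stop the calculation.** The analyst may judge visit draws inadequate and report no AUC. That is possible, but the condition states no criterion and does not exclude visit samples, so the written rule still permits the calculation.
- **The details may be elsewhere.** The SAP leaves PK to other parties, and a separate plan may give a Cohort 6 method. That cannot be seen here; Protocol 9.5.10 is the only written rule in these documents.
- **Little depends on it.** PK is descriptive and no error rate or sample size is affected. Protocol 3.7 bases between-cohort dosing on safety and efficacy data. This stands and limits the severity.

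Two stronger readings are tempting and should be set aside. A reader might infer that the rule overstates IV exposure because the first 24 hours include the rise to plateau. However, the protocol defines AUC0-24 openly as Css × 24 and does not call it first-day exposure, so for Cohorts 1-5 this is a labelling matter. A reader might also infer that a planned IV-versus-oral AUC comparison is spoiled; the documents plan no such comparison.

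**Conclusion.** The point holds for Cohort 6. Applied as written, the rule gives an AUC0-24 that is not valid for once-daily oral dosing with single untimed visit draws. For Cohorts 1-5 the rule is acceptable as a steady-state 24-hour AUC.

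The size and direction are not determined by the documents. Understatement is the likely direction for daytime visits, anywhere from slight to very large under the assumptions above; a long half-life or a trough reading makes it small, and including early samples can reverse it. A reader might infer a definite figure, such as oral exposure understated by a quarter to three quarters. That figure needs ka of 0.5-1.5 per hour, a peak-to-average ratio narrowed to 2.0-2.3, and draws at 14-20 h, none of which the documents state. Under those inputs the ratios are 0.62-0.75 at 14 h and 0.24-0.45 at 20 h, but they describe one slice of the plausible range.

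Severity is low to moderate: a wrong rule for one cohort, in a descriptive analysis, that is cheap to correct.

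**What to change.** Amend Protocol 9.5.10, the matching synopsis paragraph and the PK analysis plan as follows:

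- Limit Css × 24 to Cohorts 1-5 and label the result as steady-state AUC over 24 h.
- In Cohort 6, record the actual clock time of the last oral dose before each visit and of each PK sample. The diary items named in Protocol 3.4.5 and 6.2 are capsule count and fatty meal or snack; dose time should be named explicitly.
- Do not call the mean of the Day 8, 15, 22 and 29 samples Css. Report them as concentrations by time since last dose.
- Give a Cohort 6 24-hour AUC only from a population PK model.
- If a trapezoidal result is wanted from the 7 pm to 8 am samples, label it a partial AUC over 0-13 h after the first oral dose, including carry-over from the infusion. It has a 9-hour gap between 11 pm and 8 am and is not an oral AUC0-24.

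The cost is wording and time capture. No additional samples are needed.
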